# 7.2 Secondary Analyses

For each secondary analysis key group comparisons (Miniderm Novum Vs Control, Miniderm Novum Vs Miniderm 20% and Miniderm Novum Vs Diprobase) will be presented. These analyses will be carried out on the FAS only.

In all analyses, if the assumptions of the test are not met, transformations of the raw data or alternative tests will be considered and the most appropriate solution applied.

#### Skin Barrier:

The secondary analyses will compare the test treatment to no treatment and to the two reference treatments in terms of change in TEWL from baseline (Day 1) to Day 29. This will be done using ANCOVA with change (Day 29 – Day 1) as the outcome, Day 1 TEWL as a covariate, treatment as a factor and subject as a random effect.

#### **Skin Moisturisation:**

Capacitance and skin surface dryness (Day 29-Day 1) will be analysed using an ANCOVA as described for TEWL above.

The test treatment will be compared to no treatment and to the two reference treatments in terms of skin moisturisation (NMF) at Day 29. This will be done using ANOVA with Day 29 NMF as the outcome, treatment as a factor and subject as a random effect. The samples representing different depths will be analysed separately.

# **Tolerability:**

Patient tolerability scores will not be recorded prior to treatment and so will be summarised by time point (Day 1, Day 5 and Day 29) and the treatments compared using repeated measures ANOVA with score as the outcome, visit (Day 1, Day 15 or Day 29) and treatment as factors and subject as a random effect.

Tolerability scores as measured by investigator visual scores for redness and objective erythema from 2D colour skin images will be analysed including the observations from day 15 and 29, adjusting for baseline as necessary. This analysis will use a repeated measures ANOVA with change from baseline as the outcome, visit (Day 15 or Day 29) and treatment as factors, day 1 as a covariate and subject as a random effect.

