Invisible skin reactions to topically applied drugs and cosmetics are a common problem among subjects who consider their skin as sensitive. The reactions are often purely sensory phenomena without clinical expression, making dermatologist or instrumental evaluation

Confidential Page 45 of 65

Version: Version 3.0 Date: 15 August 2019 Sponsor: ACO Hud Nordic AB Study Code: Novum ACO-CT-2018-01 EudraCT No.: 2018-002945-12

impossible. One test method for evaluation of smarting / stinging potential is the grading by the subjects themselves (45). The participants are asked to mark in their diary on a 10 cm visual analogue scale (VAS) the degree of subjective discomfort following the use of the test creams. 0 cm represents no discomfort at all and 10 cm the worst possible state. It is considered more appropriate that the grading is performed at the participants' home rather than during the clinical visit since the participant will probably give a more accurate rating in conjunction to the application of the creams. The degree of discomfort will be graded and evaluated in the beginning, after 5 days and at the end of the study.

The criteria used to describe response are widely used and considered to be reliable.

Confidential Page 46 of 65

Version: Version 3.0 Date: 15 August 2019 Sponsor: ACO Hud Nordic AB Study Code: Novum ACO-CT-2018-01 EudraCT No.: 2018-002945-12

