## 13.1.4 Primary Efficacy Analysis

The primary analysis will compare the test treatment to no treatment and to the two reference creams in terms of change in TEWL and redness between days 31 and 29.

The statistical analysis technique used must take account of the design of the study, such that each participant has four 'matched' treatment areas. In addition, the choice of analysis must consider the distribution of the data, as it is likely that both TEWL and redness score will be skewed. Therefore, both transformations combined with parametric tests and non-parametric tests which take account of the 'matched' nature of the data will be considered. Where possible and appropriate the baseline values will be included as a covariate. Further details will be outlined in the SAP.

These analyses will be carried out on the FAS and PPS.

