# 6.2 Secondary endpoints

- Outcome relating to the resting strength of the skin barrier:
  - o TEWL after 4 weeks treatment (Day 29 Day 1)
- Outcomes relating to the skin moisturisation:
  - o Capacitance measurements (Day 29 Day 1)
  - Skin surface dryness (3D skin images) (Day 29 Day 1)
  - o NMF levels (Day 29)
- Outcomes relating to tolerability:
  - o Participant tolerability scores by VAS (Day1, Day 5, Day 29)
  - o Investigator visual scores for redness (Day 15 and Day 29, adjusted for Day 1)
  - Objective erythema from 2D colour skin images (Day 15 and Day 29, adjusted for Day1)
- Outcome relating to cream consumption:
  - o Cream consumption (g) (Day 1, Day 5, Day 15 & Day 29)
- Outcome relating to safety:
  - Number of adverse events (Screening, Day 1, Day 5, Day 15, Day 29 and Day 31)

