#### **Redness**

Visual scoring of subject's skin by an expert will take place at 4 weeks (Day 29) and after skin irritation (Day 31). Scores will be on a scale from 0 to 3.

Objective scoring of the sites will also be measured using a mexameter. Triplicate recordings will be made; the average reading for each patient at each time point at each site will be used in the analysis.

Change will be calculated as post-irritation observation – 4 week observation (Day 31 – Day 29).

Secondary endpoint: Erythema index from 2d imaging will be measured at baseline and on days 15, 29 and 31.

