# 7.5 Multiplicity considerations

All analyses in this SAP will be carried out with a two sided 5% significance level.

Secondary analyses are considered to be exploratory and so no adjustment will be made for multiplicity.

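### The tolerability models for VAS and 2D erythema have no area-level random effect, so treatment contrasts are tested against the wrong error term; standard errors may be too small or too large

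*SAP*

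**What the plan says.** Under Tolerability, SAP 7.2 gives two repeated measures models. The VAS model has "visit (Day 1, Day 15 or Day 29) and treatment as factors and subject as a random effect". The model for redness and erythema takes change from baseline as outcome, with "visit (Day 15 or Day 29) and treatment as factors, day 1 as a covariate and subject as a random effect". Neither names an area-within-subject term, a covariance for visits within an area, or a treatment-by-visit term.

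Protocol 10.2 randomises treatments to test sites, and Protocol 13.1.4 notes that "each participant has four 'matched' treatment areas". SAP 6.2 lists the repeated readings: "Participant tolerability scores by VAS (Day1, Day 5, Day 29") and "Objective erythema from 2D colour skin images (Day 15 and Day 29, adjusted for Day1"). According to Protocol 11.5 the VAS rates "the degree of subjective discomfort following the use of the test creams", so it may be scored for three areas rather than four.

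On testing, SAP 7.5 states: "All analyses in this SAP will be carried out with a two sided 5% significance level". The same section calls the secondary analyses exploratory and makes no multiplicity adjustment.

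**The concern.** There are two levels of clustering: areas within a person, and visits within an area. Because treatment is allocated to the area, area-to-area variation within a person is the noise against which treatments must be judged, and repeat visits are subsamples of an area. A random subject effect covers only the first level. That is enough for the primary model and for the TEWL, capacitance, dryness and NMF models, which use one value per area. The tolerability models carry the same random term over to two or three values per area.

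The SAP's fallback when assumptions fail is generic and does not mention correlation within an area. The protocol's instruction to respect the matched areas does not mention repeat visits.

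Tolerability is a stated secondary objective. Protocol 5.4 names it beside barrier strengthening as what to establish before studies in children, and Protocol 5.5 cites less stinging as a potential benefit. The confidence intervals for the test cream against each comparator should therefore have their nominal coverage.

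**Working it through.** **Inputs.** From the documents: T areas per person (4 for erythema; 3 for the VAS if only creams are scored), m visits per area (VAS 3, erythema 2 after baseline), two-sided alpha 0.05. The documents state no precision or power figure for these models, so there is none to reproduce. Not in the documents, and therefore assumed:
- A: subject-by-area variance. With one area per treatment in each person, this is the same as subject-by-treatment variance.
- V: subject-by-visit variance.
- E: residual variance.
- Area share rho = A/(A+E), taken from 0.2 to 0.5 with A+E = 1.

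**Formulas (balanced data, no covariate).**
- True variance of a treatment contrast: 2(E + mA)/(nm). V cancels, because it is common to all areas at a visit.
- Variance reported by the subject-only model: 2{E + [(T-1)mA + (m-1)TV]/(Tm-1)}/(nm).
- k = true SE / model SE, the square root of the ratio. The sample size cancels, so n = 40 and n = 50 give the same k.
- Type I error = 2[1 - Phi(1.96/k)].
- The model SE is too small exactly when V < mA.

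**VAS, T = 3, m = 3.** The model term is E + 0.75A + 0.75V.

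| rho | V | E + 3A | model term | k | type I error |
|---|---|---|---|---|---|
| 0.2 | 0 | 1.40 | 0.95 | 1.21 | 10.6% |
| 0.3 | 0 | 1.60 | 0.925 | 1.32 | 13.6% |
| 0.5 | 0 | 2.00 | 0.875 | 1.51 | 19.5% |
| 0.2 | 0.2 (= A) | 1.40 | 1.10 | 1.13 | 8.2% |
| 0.5 | 0.5 (= A) | 2.00 | 1.25 | 1.26 | 12.1% |
| 0.2 | 0.8 | 1.40 | 1.55 | 0.95 | 3.9% |

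If the untreated area is scored too (T = 4), V = 0 gives 10.4% at share 0.2 and 18.6% at 0.5.

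**2D erythema, T = 4, m = 2, no covariate, V = 0.**
- Share 0.2: true term 0.8 + 0.4 = 1.2; model term 0.8 + 1.2/7 = 0.971; k = 1.11; type I error 7.8%.
- Share 0.5: true term 1.5; model term 0.5 + 3/7 = 0.929; k = 1.27; type I error 12.3%.

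**2D erythema with the Day 1 covariate, as the SAP specifies.** Day 1 on the same area absorbs part of A, so this case was simulated (n = 40, 3,000 runs, A = E = 0.5).
- V = 0: actual SD 0.1577, model SE 0.1338, ratio 1.18, type I error 9.4%. A separate run at n = 50 gave 9.1%.
- V = 0.5: 0.1575 against 0.1580, type I error 5.6%. At n = 50 with V = A, the results were 5.7%, 6.2% and 5.3% at shares 0.2, 0.3 and 0.5.
- V = 1.0: 0.1581 against 0.1796, type I error 3.0%.

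**Effect of the remedy.** Testing against the area-level error gave 4.6% to 5.7% in all simulated VAS and erythema cases at n = 40.

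**Why an area term alone is not enough.** Without a subject-by-visit term, V enters the within-area residual, whose expectation becomes E + V. The fitted area variance then estimates [(E + mA) - (E + V)]/m = A - V/m. At A = 0.2, V = 0.8, m = 3 this is 0.2 - 0.267 = -0.067. Software that holds variances at or above zero would set it to zero and return to the subject-only analysis.

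**Visits and scope.** The VAS is collected and summarised at Days 1, 5 and 29, but the model names Days 1, 15 and 29, and SAP 6.4 equates five days of treatment with Day 15. For visual redness, SAP 6.4 says: "Visual scoring of subject's skin by an expert will take place at 4 weeks (Day 29) and after skin irritation (Day 31"). Both protocol schedules (Tables 1 and 2) agree. With no Day 1 or Day 15 score, the visual-redness model cannot be fitted as written, so the calculation covers the VAS and 2D erythema only.

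**The case against.** The strongest objection is that the direction of the error is not fixed. A reader might infer that the standard errors are always too small, but that follows only if subject-by-visit variance is small. Such variance is plausible: one person scores all the creams at each diary time, and all areas are imaged at one visit in a room allowed to vary over 21 ± 2 °C and 38-50% humidity. It cancels from treatment contrasts but inflates the pooled residual. This stands: for the VAS it removes the excess once V reaches 3A, and for erythema with the covariate at about V = A. It does not rescue the specification, because a larger V makes the test conservative.

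A reader might also infer that repeat readings are treated as independent. They are not: the subject effect gives all of one person's readings a common correlation. What is missing is the extra correlation within an area.

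The name repeated measures ANOVA could cover an analysis with a subject-by-treatment error stratum or a visit covariance. That is fair, but the SAP does not say so, and as written only subject is random.

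Two further points hold. A visit-averaged contrast is a legitimate target and the VAS is summarised at each visit, so the missing treatment-by-visit term is a matter of choice. And since these analyses are labelled exploratory, no confirmatory claim depends on them.

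**Conclusion.** The point holds for the VAS and 2D erythema models: as written, treatment contrasts use a pooled residual instead of the area-level error. Under the assumed area shares of 0.2 to 0.5, VAS type I error is about 11-20% with no subject-by-visit variance, about 8-12% when that variance equals the area variance, and about 4% when it is 0.8 at share 0.2. Erythema is about 8-12% without the covariate and without subject-by-visit variance. With the Day 1 covariate it is about 9% at share 0.5, and near nominal when V = A. Every figure rests on assumed variance components, so the documents support miscalibration of unknown direction and not a definite inflation. The VAS is the more exposed of the two, since a person's reaction to a given cream may well persist across visits. The primary analysis and the one-value-per-area secondary analyses are unaffected.

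**What to change.** In SAP 7.2, Tolerability, for the VAS and 2D erythema models:
- Add a subject-by-treatment (area within subject) random effect together with a subject-by-visit random effect, or an equivalent explicit covariance.
- State that treatment contrasts are tested against the area-level error.
- Make the VAS visits in the model, and in SAP 6.4, match those collected.
- State whether the untreated area is scored on the VAS.

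A treatment-by-visit term is optional. For visual redness, reconcile the planned analysis with the schedule of scores before specifying any model.

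The cost is a line or two of wording and one or two extra model terms, with no new data. Intervals may widen or narrow, depending on which variance component dominates.

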#### **Consumption:**

The total consumption of the creams (test or reference cream), based on cream weight will be calculated and tabulated descriptively. The planned dose is 0.5g per application (2 applications per day), if consumption is twice or half that expected over the study this will be flagged. If appropriate, consideration will be given to including the cream consumption as a covariate in the model or in an exploratory analysis of the primary endpoints.

# 7.3 Tertiary Analysis

The number of FLG loss-of-function mutation carriers will be summarised. If sufficient participants with the mutation are detected then descriptive tabulations of TEWL by mutation status will be presented.

#### 7.4 Adverse event data:

All Adverse Events will be summarized for all subjects enrolled in the study – both the number of participants with an AE and the total number of AEs. AEs will be tabulation by system organ class and by preferred term, as well as severity and relationship to treatment. Finally, those AEs which are specifically recorded as related to one of the test sites, the AEs will be summarised by test site. A listing, by participant number, will be produced to show the AEs with the worst severity and worst relationship to treatment.

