#### 10.2 Method of Assigning Participants to Treatment Groups

Randomisation (allocation of the treatments to the test sites) will be performed according to a randomisation list with balanced allocation to the 4 different test areas (to avoid site-dependent effects). Participants eligible for the study will be provided with a participant ID number at Visit 1.

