#### 13.1.9 Adverse Events

AEs will be coded using the Medical Dictionary for Regulatory Activities and tabulated by system organ class and by preferred term.

Sponsor: ACO Hud Nordic AB

EudraCT No.: 2018-002945-12

Study Code: Novum ACO-CT-2018-01

The total number of participants with at least 1 AE and the total number of AEs will be presented.

The number of participants and the number of AEs will be tabulated by system organ class and by preferred term. AEs will also be tabulated versus worst severity and worst relationship to treatment. Finally, for those AEs which are specifically recorded as related to one of the test sites the AEs will be summarised by test site. A listing, by participant number, will also be produced which lists the AEs with worst severity and worst relationship to treatment.

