# 2. Study Methods

# 2.1 Study Design

It is planned to recruit 40 adults (male and female, aged 18 and above) with personal history of atopic dermatitis but no current eczema on the volar forearms and no possible allergy to the ingredients in the study medications.

Four treatment sites on the lower volar forearms (two on the right and two on the left) will be randomised for each participant with one treatment to be applied to each of three sites and the fourth remaining untreated as a control. The four treatment groups are;

- No treatment (control)
- Miniderm Novum (test cream)
- Miniderm 20% (reference cream)
- Diprobase (reference cream)

One Finger Tip Unit (FTU) of each cream will be applied twice daily on the designated study area. The participants will record details of cream application frequency, as well as participant tolerability in a diary.

Subjects will remain in the study for 4-5 weeks.

At each study visit, concomitant medication and any AEs are noted in the Case Report Form (CRF). The study medication will be collected and weighed in order to estimate cream consumption.

Participants will attend 5 clinic visits during the study:

- Visit 1 (screening) will be performed at baseline (Day 1)
- Visit 2 will be performed after 5 days of treatment
- Visit 3 will be performed after 15 days of treatment

- Visit 4 will be performed after 29 days of treatment
- Visit 5 will be performed 1 day after SLS-patch removal (Day 31)

Assessors will be blind to the treatment assigned to each site. Subjects will be blinded to the cream assigned to each study site – although the untreated site will remain unblinded.

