# 4.2 Secondary objective:

To determine whether there is a difference between the new moisturising cream (the test cream) and (1) no treatment and (2) the two reference creams in:

- Resting skin barrier function
- Skin moisturisation
- Tolerability
- Cream consumption
- Safety

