#### 6.4 Variables

#### **TEWL**

Triplicate measurements will be performed at each test site (upper part of the right and left lower volar forearm and lower part of the right and left lower volar forearm) at baseline (Day 1), after 4 weeks treatment (Day 29) and after skin irritation (Day 31) using an AquaFlux condensing chamber probe. A fourth measurement may be taken if the technician feels that one of the previous readings was abnormal. The average reading for each patient at each time point at each site will be used in the analysis.

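### Site-related adverse events are summarised only by anatomical position, so no specified AE table compares the creams

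*SAP*

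**What the plan says.** SAP 7.4 sets out the AE summaries: overall numbers of participants and events, then breakdowns by MedDRA class and term, severity and relationship to treatment. For local events it adds "those AEs which are specifically recorded as related to one of the test sites, the AEs will be summarised by test site". Protocol 13.1.9 has the same rule: "for those AEs which are specifically recorded as related to one of the test sites the AEs will be summarised by test site".

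The SAP's TEWL paragraph (section 6.4) shows what a test site is: "each test site (upper part of the right and left lower volar forearm and lower part of the right and left lower volar forearm". Both documents treat the site and the treatment placed on it as separate things. Protocol 10.2 describes "Randomisation (allocation of the treatments to the test sites" and a "randomisation list with balanced allocation to the 4 different test areas (to avoid site-dependent effects". SAP 2.1 states that "Assessors will be blind to the treatment assigned to each site".

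The objective these data serve is comparative. SAP 4.2 begins "To determine whether there is a difference between the new moisturising cream (the test cream) and (1) no treatment", continues with the two reference creams, and includes safety in the list that follows. SAP 6.2 makes the number of adverse events the safety endpoint.

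In SAP section 8 the AE tables are 14.3.1 (participants with AEs), 14.3.2 (class and term) and an open 14.3.x entry for further tables as needed. None is specified by treatment.

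**The concern.** Every participant receives all four conditions, so an AE counted per participant cannot be attributed to one cream. The AEs that can be attributed are those tied to a single treated area. The plan tabulates these by the factor over which treatment was deliberately balanced, not by treatment.

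A programmer following the SAP would produce four columns: upper right, lower right, upper left and lower left. Each would contain about a quarter test cream, a quarter of each reference cream and a quarter untreated skin. Such a table can say something about forearm position. It cannot say whether the test cream causes more local events than no treatment or than either reference cream, and that is what the secondary objective asks. The test cream is unmarketed and Protocol 5.4 foresees later trials in children and infants, so the comparison is worth having in the report in a form fixed in advance.

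**Working it through.** The plan states no figure here, so there is none to reproduce. The check has two parts.

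**1. Does any specified AE summary identify the cream?**

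- Class, term and severity do not refer to a cream.
- Relationship to treatment is a causality grade (probable, possible or unlikely in Protocol 12.2). It does not say which cream was on the area.
- Test site is an anatomical position (SAP 6.4). Protocol 14.2 likewise pairs the term with anatomical site when describing how images are filed.
- Table 14.3.x is open-ended and commits to nothing.

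So none does.

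**2. What does a by-position table show under balanced allocation?**

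Let p1 to p4 be the risks of a local AE on an area under the four conditions. With balanced allocation each condition occupies each position in a quarter of participants, so for every position

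expected rate = (p1 + p2 + p3 + p4) / 4.

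The contrast between conditions cancels. If a position also adds its own fixed amount to the risk, the columns differ by that amount, but the difference is still not a treatment effect.

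The documents give no AE rates. The following are **assumptions**: untreated 2%, each reference cream 5%, and test cream 10%, 20% or 40%. N = 40 is the SAP 2.1 figure. Expected numbers of areas with a local AE:

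| Test-cream risk | Mean of four | Each position (40 × mean) | Untreated | Test cream | Each reference cream |
|---|---|---|---|---|---|
| 10% | (2+10+5+5)/4 = 5.5% | 2.2 | 0.8 | 4.0 | 2.0 |
| 20% | (2+20+5+5)/4 = 8.0% | 3.2 | 0.8 | 8.0 | 2.0 |
| 40% | (2+40+5+5)/4 = 13.0% | 5.2 | 0.8 | 16.0 | 2.0 |

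The right-hand columns are 40 × the assumed risk. A simulation of 4,000 trials with Latin-square allocation agrees. At 20% it gave 3.19 to 3.24 at the four positions, against 0.80, 8.06, 1.99 and 2.00 by treatment.

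The protocol recruits 50, which is not a multiple of four. Twelve complete squares contribute 12 × 0.32 = 3.84 per position at the 20% assumption. If the two remaining participants take consecutive rows of the square, they add 0.22, 0.25, 0.10 and 0.07, giving 4.06, 4.09, 3.94 and 3.91. By treatment the expected counts are 1.0, 10.0, 2.5 and 2.5. The by-position table stays almost flat.

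**The case against.** The strongest reply is that test site may be shorthand for the treated area. The documents use the term loosely: in places it means the clinic (Protocol 9.8 and 11.2.11), and the four areas are also called treatment sites or treatment areas. The authors may have intended a by-treatment table. That is possible, but where the term refers to skin, the documents define it by position and speak of treatments being assigned to it. No place was found where it means the treatment. The wording needs correcting even if the intention was sound.

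A reader might go further and infer that a local reaction to the test cream would be hidden. The documents do not support that:

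- SAP 7.2 compares participant VAS scores, visual redness and 2D erythema between treatments.
- AEs are listed individually (listing 16.2.7).
- SAP 2.2 gives the statistician the full key at database lock, so each site can be mapped to its treatment.
- Table 14.3.x leaves room for a by-treatment table.

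These points stand and limit the concern to the specified AE tables. They do not remove it, because a stated objective should not depend on an optional table or on the reader matching a listing to the key.

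Three further points stand. Systemic AEs cannot be assigned to one cream in this design, so summarising them overall is right. SAP 7.5 treats secondary analyses as exploratory, so no confirmatory claim rests on this table. Position also has some interest of its own: SAP 7.9 records that skin may react differently along the forearm, so a by-position summary need not be dropped.

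**Conclusion.** The point holds for the planned AE summary and no further. As written, both documents summarise site-related AEs only by a factor that is balanced against treatment, and no specified AE table compares the creams although an objective requires it.

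The cancellation rests on balanced allocation and on test site meaning position, both of which are in the documents. It does not depend on the assumed rates or on N. The counts do depend on the assumed rates: they show how the table behaves and do not forecast events in this trial. They are also expectations, so observed counts in a trial of 40 to 50 people would vary between positions by chance.

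The information is recoverable after unblinding, provided that the site of each local AE is recorded. This is a defect in specification that should be corrected. It is not a loss of safety data and does not touch the primary analysis.

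**What to change.** In SAP 7.4 and Protocol 13.1.9, replace the by-test-site rule with wording such as:

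> AEs recorded as related to a test site will be summarised by the treatment applied at that site (Miniderm Novum, Miniderm 20%, Diprobase, untreated), giving numbers of participants and of events, in the safety set. A summary by anatomical position may be added. All other AEs will be summarised overall.

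Name the table in SAP section 8 in place of relying on the 14.3.x entry. If the protocol is not amended, Protocol 13.3 already provides for describing and justifying the change in a revised SAP and the final report.

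Confirm that the AE form records the test site. Both documents presuppose this, but the AE fields listed in Protocol 12.2 do not include it, and the form itself is only named in Protocol Appendix A. If it is not captured, the field has to be added or recovered from the diaries where possible.

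The cost is one more table, a sentence in each document and a check of the AE form. The mapping from site to treatment comes from the randomisation key that the statistician receives in any case.
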